Data will be handled according to national laws on data protection (in Denmark including the General Data Protection Regulation and the Data Protection Act). In Denmark, the project is registered with the Central Denmark Region's internal list of research projects. Data will be used for the purpose outlined in this trial protocol.

20. Adherence

We have defined adherence as those participants in the vaginal cerclage group who receives a vaginal cerclage before 16+0 weeks of pregnancy and those participants in the laparoscopic cerclage group who receives a laparoscopic cerclage before 10+0 weeks of pregnancy. Subsequent exam-indicated vaginal cerclage in either group will count as adherent.

21. Analyses

All estimates of differences between groups will be presented with two-sided 95% confidence intervals, unless otherwise stated. For the primary outcome of preterm birth, a p-value will be produced, with statistical significance considered at the 5% level.

For the second prioritized primary outcome of baby death, we will incorporate a conditional hierarchical approach to hypothesis testing to ensure we appropriately control for the overall rate of type I error(5). If the primary outcome of preterm birth meets a superiority conclusion in favour of either a vaginal or laparoscopic cerclage, we will then proceed to examine any differences between the two procedures for baby death. If the p-value from this test (baby death) is less than or equal to 0.05 in the model (or if the 95% confidence interval does not contain one) we will declare superiority for this outcome.

Other secondary outcomes will be considered as exploratory; no adjustment for multiple comparisons will be made and hence significance should not be inferred from the confidence interval width.

All primary analyses (primary and secondary outcomes) will be conducted on a modified intention-totreat basis only including patients who are pregnant at time of randomisation or become pregnant

after randomisation and carry a pregnancy beyond 14+0 weeks. Participants who have an early miscarriage will be excluded post randomisation, unless they have a viable pregnancy beyond 14+0 weeks later in the study period. The rationale behind this decision is, that an early miscarriage is unlikely to be caused by an incompetent cervix. Participants will be analysed in the intervention group to which they were randomised, and all participants shall be included whether or not they received the allocated intervention.

A secondary per protocol and as-treated analysis will be performed for each treatment group for the primary outcomes only (see section 20 for description of whom will perform the per protocol analysis).

Presentation of the quantitative data from the internal pilot will largely consist of descriptive statistics and comparisons between the two groups. The inclusion number will be described according to country, site, and groups in Table 1. The reasons for ineligibility, refusal, loss to follow-up, or missing data will be categorised and described as overall frequencies per country, site, and according to groups in Table 1. No outcome data will be available for evaluation.

Subgroup analyses will be conducted to determine whether there are signs of an effect for each prespecified subgroups. To ensure validity to the subgroup analysis, the factors considered for subgroup analyses is pre-specified below:

- Participants with a history of emergency/laboring caesarean section followed by a spontaneous singleton late miscarriage or preterm birth 14+0-28+0 weeks.
- Participants with a prior elective vaginal cerclage placement but nonetheless a spontaneous late miscarriage or PTB between 14+0 and 28+0* weeks
- History of a prior emergency cerclage with delivery between 14+0 and 28+0* weeks
- Participants with a history of one or more deliveries between gestational age 16+0 to 28 +0 and a clinical diagnosis of cervical insufficiency.
- Any conization and a short pre-pregnancy cervix (e.g. short ectocervix with inspection or below 15-20 mm with ultrasound)
- History of three or more deliveries GA 16+0 to 36+6 weeks

The statistical analyses and reporting will adhere to the Consolidated Standards of Reporting Trials (CONSORT)-guidelines[23, 24].

STATA and 'R' will be used for data management and analyses.

Patient inclusion and exclusion will be illustrated in a modified CONSORT flow diagram for non-pharmacologic trials[25] (see figure 1).

See the full analysis plan for further details.

22. Monitoring and oversight

The trial is monitored according to Good Clinical Practice (GCP) standards.

A decision as to perform an interim analysis will made after the internal pilot period. The data monitoring committee will evaluate pilot data as described above presented by the PI at the ending of the internal pilot after 18 months of inclusion.

In the full trial, there will be no predefined stopping criteria, and criteria for termination will be at the discretion of the trial steering committee and the Trial Sponsor.

Three independent members have been appointed to a Trial Steering Committee (TSC) prior to commencement.

The role of the TSC is to provide independent overall supervision for the trial on behalf of the NORACT board including advice on

- Protocol elaboration
- Problems occurring during the study
- o Interpretation of the results

Three independent members have been appointed to the Independent Data Monitoring Committee (IDMC) prior to commencement.

- The IDMC members are to safeguard the interests of trial participants, assess the safety of the intervention during the trial, and monitor the overall conduct of the clinical trial.
- The NORACT board will review de-identified data for safety at predetermined milestones (approximately halfway through the inclusion) but can – at any time – require extra reviews. After the reviews, the IDMC will create a short report to the TSC with recommendations for continuation, modifications, or termination of the trial.

Charters describing the roles and responsibilities of the IDMC and the TSC, including the timings of meetings, methods of providing information between the IDMC and the TSC, frequency and format of meetings, statistical issues and relationships with other committees have been approved and signed. See appendix 1 for the signed declarations.

23. Ethics and dissemination

The study will be conducted in accordance with the ethical principles outlined in the latest version of the 'Declaration of Helsinki' and the 'Guideline for Good Clinical Practice' related to experiments on humans. Approval of the study will be sought from the Central Denmark Region Committees on Health Research Ethics. The results of the study will be reported according to the CONSORT 2010 statement.

Any possible risks associated with the conduct of the trial are not, neither on their own nor compared to the expected gain from the trial, expected to reach an indefensible extent. The therapeutic and public health gain of the trial is expected to justify the trial. The sake of the trial participants will at any time override the sake of the conduct of the trial. The results of this trial have the potential to generate important knowledge for the improvement of PTB and the potentially lower the mortality and morbidity caused by PTB in future high risk pregnancies.

24. Patient and public involvement

Prior to the NORACT study, we will perform a qualitative study in women with vaginal and laparoscopic cerclages on their experience, information, and preference for a cerclage. An individual protocol for this study will be drafted.

We will seek to form a formal patient representative group with members from at least two countries to participate in the management of the study, the information distributed to eligible participants, and the dissemination of the results.

25. Declaration of interests

None of the protocol authors has conflicts of interest to declare.

26. Publication

Positive, inconclusive as well as negative results from the trial will be published in peer reviewed international scientific journals. The trial coordinating investigator will draft these papers as first author, and principal investigator [name] will be last corresponding author. Additional authorship will follow standard authorship guidelines and will include all members of the NORACT board and the representatives from the secondary and tertiary trial sites according to a prespecified list of types of engagement.

27. Access to data

After publication of the trial results, the final dataset will be publicly available in an anonymized form using i.e. Zenodo open data repository (CERN) or another equivalent database.

28. Ancillary and post-trial care

In Denmark, participants taking part in clinical studies are insured during and after the trial according to the Act on Patient Safety in the Danish Health Care System.

29. Abbreviations

ART – Assisted reproductive therapy

- BMI Body mass index
- CNS Central Nervous System
- CS Caesarean section
- eCRF electronic Case Record Form
- FDCS Full dilatation caesarean section
- GA gestational age
- GCP Good Clinical Practice
- GDPR General Data Protection Regulation
- IDMC Independent Data Monitoring Committee

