11.1 Intervention: Laparoscopic cerclage

Anesthesia: General.

Timing: Pre-pregnancy.

In unplanned pregnant, but already randomized women, or in women who are identified during pregnancy up till 10+0 weeks of gestation.

Surgical access: Classic or robot-assisted laparoscopy.

Procedure: A manipulator is applied to the non-pregnant uterus according to local routine. Detachment of the bladder peritoneum and bladder, and dissection of the uterine artery are performed at the surgeon's discretion. Non-absorbable woven band or sutures 0-1-2 are used for the cerclage according to local routine.

The cerclage suture is placed in the cervico-corporal angle medial to the uterine arteries. The suture is performed by the Endoclose needle technique [14], an armed suture or band [15, 16] or the Dechamps needle technique [17] with anterior or posterior knots according to local routine. The knot is tied with appropriate tension to fit the suture to the cervical tissue according to the surgeon's discretion.

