11.2 Comparison: Vaginal cerclage

Anesthesia: Regional (or general if necessary)

Timing: During pregnancy; from identification of fetal heart rate activity to 16+0 weeks' gestation. The clinician decides whether to wait for normal nuchal translucency scan results before the operation. Procedure: Ensure viability of the fetus with ultrasound. The needle is passed through the collum substance and mucosa four to eight times and must include enough tissue to withstand the strain of pregnancy. Penetration of the cervical canal is avoided.

Choice of suture material is at the discretion of the surgeon [18].

The suture is placed ad modum McDonald (low) "as high as possible" [19]. If necessary, a Shirodkar (high) procedure is acceptable as an intraoperative decision.

An extra stitch can be placed, if a second stitch can be placed in a more cranial position than the first stitch.

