 - Time frame: From time of randomisation to 42 days after delivery
- Maternal morbidity surgery related.
 - Definition: Admission to ICU or a unit that provides 24-h medical supervision and can provide mechanical ventilation or continuous vasoactive drug support within 30 days of the cerclage procedure.
 - Time frame: 30 days after cerclage procedure
- Maternal morbidity pregnancy related.
 - Definition: Admission to ICU or a unit that provides 24-h medical supervision and can provide mechanical ventilation or continuous vasoactive drug support at any point during pregnancy through 42 days postpartum for pregnancy or childbirth related complications[20]
 - Time frame: From time of randomisation to 42 days after delivery
- Harm to participant surgery related.
 - Definition:
 - Damage to internal organs (yes/no)

- Need for re-operation (yes/no)
- Thromboembolic events (defined as deep vein thrombosis, pulmonary embolism or stroke) (yes/no)
- Maternal cardiopulmonary arrest (yes/no)
- Time frame: 30 days after cerclage procedure.
- Harm to participant
 - Definition:
 - Damage to internal organs (yes/no)
 - Need for re-operation (yes/no)
 - Thromboembolic events (defined as deep vein thrombosis, pulmonary embolism or stroke) (yes/no)
 - Maternal cardiopulmonary arrest (yes/no)
 - o Time frame: From time of randomisation to 42 days after delivery
- Bleeding surgery related.
 - Definition: Blood loss >500 milliliters
 - Time frame: 30 days after cerclage procedure
- Bleeding pregnancy related.
 - Definition_ Blood loss > 1000 milliliters
 - o Time frame: From time of cerclage procedure to 42 days after delivery
- Maternal infection[9] surgery related.
 - o Definition: Infection leading to antibiotic treatment
 - Time frame: 30 days after cerclage procedure
- Maternal infection[9] pregnancy related.
 - o Definition: Infection leading to antibiotic treatment
 - Time frame: From time of cerclage procedure to 42 days after delivery
- Maternal serious infection[9] surgery related.
 - o Definition: Infection leading to ICU admission
 - Time frame: 30 days after cerclage procedure
- Maternal serious infection[9] pregnancy related.
 - Definition: Infection leading to ICU admission
 - Time frame: From time of cerclage procedure to 42 days after delivery
- Preterm prelabour rupture of membranes[9]
 - Rupture of membranes before 37 weeks of gestation
 - o Time frame: At birth
- Threatened preterm labour
 - \circ $\;$ Definition: Leading to admission and intervention.

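### Pregnancy-related bleeding and infection are counted from the cerclage procedure, so the length of observation depends on the allocated arm and is generally longer with laparoscopy

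*Protocol*

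**What the plan says.** Protocol section 12 lists bleeding, infection and serious infection twice each: once as surgery related (30 days after the procedure) and once as pregnancy related. All three pregnancy-related versions have the same window: "Time frame: From time of cerclage procedure to 42 days after delivery". Their definitions are "Blood loss > 1000 milliliters", "Definition: Infection leading to antibiotic treatment", and infection leading to ICU admission. None of these definitions contains a limit to pregnancy.

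The date of the procedure is set by arm:

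- Laparoscopic (section 11.1): "Timing: Pre-pregnancy", with the exception "In unplanned pregnant, but already randomized women, or in women who are identified during pregnancy up till 10+0 weeks of gestation".
- Vaginal (section 11.2): "During pregnancy; from identification of fetal heart rate activity to 16+0 weeks' gestation".

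Sections 14 and 16 describe women being identified at a pre-pregnancy consultation, so the pre-pregnancy laparoscopy appears to be the usual case.

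Other entries in the same list start at randomisation: maternal mortality, pregnancy-related morbidity and general harm. The definition of pregnancy-related morbidity is also bounded to events "at any point during pregnancy through 42 days postpartum for pregnancy or childbirth related complications".

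Section 21 keeps women in the analysis whether or not they received the allocated procedure. It also lets a woman who miscarries early qualify through a later pregnancy that passes 14+0 weeks.

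**The concern.** A fair comparison of event risks needs follow-up to start at the same point in both arms. Here it starts at an event whose timing the allocation determines. A woman operated on laparoscopically before pregnancy is counted through the time to conception, early pregnancy, the rest of pregnancy and six weeks after delivery. A woman in the vaginal arm is counted only from her procedure in pregnancy. With identical true rates in the two arms, the arm watched for longer shows more events.

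Two further problems come from the same start point. A woman who receives no cerclage stays in the analysis but has no start date. And a laparoscopic clock that started before conception keeps running through an early miscarriage until the later qualifying pregnancy.

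What is at stake is the maternal side of the comparison. Section 7 makes maternal adverse outcomes part of the full-trial objective, and the background frames the question as effectiveness weighed against the disadvantages of each procedure.

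**Working it through.** The protocol states no window length or ratio, so there is no figure of its own to reproduce. The check is to work out the windows its rules imply.

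**Inputs from the protocol.** The window starts at the procedure and ends 42 days (6 weeks) after delivery. Laparoscopy is before pregnancy, or up to 10+0 weeks. Vaginal cerclage is from fetal heart activity to 16+0 weeks.

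**Assumptions (not in the protocol).** Delivery at D = 38 weeks. Conception at 2 weeks of gestational age. Time from laparoscopy to conception T = 0 to 52 weeks. Vaginal procedure at g = 6, 12 or 16 weeks, with 6 standing for the earliest fetal heart activity.

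**Formulas, in weeks**

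- Vaginal: V = (D − g) + 6
- Laparoscopic before pregnancy: L = T + (D − 2) + 6
- Laparoscopic in pregnancy at gestation h: L = (D − h) + 6

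**Windows.** V = 38 (g = 6), 32 (g = 12) and 28 (g = 16). L before pregnancy = 42 + T. L at 10+0 = (38 − 10) + 6 = 34.

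**Ratio L / V**

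| Laparoscopic procedure | L | g = 6 | g = 12 | g = 16 |
|---|---|---|---|---|
| Before pregnancy, T = 0 | 42 | 1.11 | 1.31 | 1.50 |
| Before pregnancy, T = 13 | 55 | 1.45 | 1.72 | 1.96 |
| Before pregnancy, T = 26 | 68 | 1.79 | 2.12 | 2.43 |
| Before pregnancy, T = 52 | 94 | 2.47 | 2.94 | 3.36 |
| In pregnancy, 10+0 | 34 | 0.89 | 1.06 | 1.21 |

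The row T = 0 also gives the result if pregnancy related is read as excluding everything before conception. The woman operated on before pregnancy is then counted from conception, the vaginal-arm woman still only from her procedure, and the ratio is 1.1 to 1.5.

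**Mixed arm.** Suppose half the laparoscopic arm is operated on in pregnancy at 8 weeks (window 36) and vaginal procedures are at 12+0 (window 32). The mean laparoscopic window is (55 + 36)/2 = 45.5 weeks for T = 13, (68 + 36)/2 = 52 for T = 26, and (94 + 36)/2 = 65 for T = 52. The ratios are 1.42, 1.62 and 2.03.

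**Effect on a risk comparison.** With an equal constant hazard in both arms, p(lap) = 1 − (1 − p(vag))^ratio. Assume a 20% risk of antibiotic-treated infection in the vaginal arm:

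- Ratio 1.1: 1 − 0.8^1.1 = 21.8%, apparent risk ratio 1.09
- Ratio 1.5: 1 − 0.8^1.5 = 28.4%, apparent risk ratio 1.42
- Ratio 2: 1 − 0.8^2 = 36.0%, apparent risk ratio 1.80

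None of these reflects a true difference. The 20% and the constant hazard are illustrations only.

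**The case against.** Four points deserve weight.

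*The label.* These outcomes are called pregnancy related and sit opposite surgery-related twins. An infection while trying to conceive is not naturally pregnancy related. Section 18 records antibiotic treatment with gestational age under the NORACT pregnancy, and refers to a data dictionary, not shown here, that may set tighter limits. This stands in part: it could remove the pre-conception months, but it leaves the 1.1 to 1.5 ratio because the vaginal clock still starts later.

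*The exceptions.* Laparoscopy up to 10+0 is allowed, and section 21 includes women pregnant at randomisation. For them the imbalance is small and can reverse (0.89 against a vaginal procedure at 6 weeks). This stands and limits any statement about the whole arm.

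*The outcomes differ.* If blood loss above 1000 ml clusters around delivery or surgery, extra months before conception add little. That is plausible, so the point bears mainly on antibiotic-treated infection. The illustration should not be carried over to bleeding or ICU infection.

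*The status.* Section 21 calls these outcomes exploratory. The 30-day surgical outcomes have equal length in both arms, and mortality, morbidity and general harm run from randomisation, so much of the maternal comparison is sound. This limits the consequence. But exploratory status deals with multiplicity, not with unequal observation, and a larger sample would not remove the bias.

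A postoperative event in the first 30 days falls in both the surgery-related and the pregnancy-related windows. This happens in both arms and is not in itself an error.

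**Conclusion.** The concern holds as a design inconsistency in three secondary, exploratory outcomes. Their observation window starts at a point fixed by allocation, while neighbouring outcomes in the same list start at randomisation, and no reason is given for the difference. Observation is generally longer with laparoscopy and the bias mostly runs against it.

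The size cannot be fixed from the protocol. Under the assumptions above, the window ratio is about 1.1 to over 3 for pre-pregnancy procedures, about 0.9 to 1.2 for laparoscopy at 10+0, and 1.1 to 1.5 on the pregnancy-bounded reading.

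A reader might infer that the laparoscopic arm is watched for about twice as long, or that infection risk would appear doubled. The documents do not support that. A ratio of 2 needs T = 2V − 42, that is 14, 22 or 34 weeks to conception for vaginal procedures at 16+0, 12+0 or 6 weeks. The protocol gives neither the time to conception, nor the usual gestation at vaginal cerclage, nor the share of laparoscopies done in pregnancy.

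The two primary outcomes and the sample size are untouched.

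**What to change.** Start all three pregnancy-related outcomes at the same arm-neutral point. Randomisation is preferable because section 12 already uses it for maternal mortality, pregnancy-related morbidity and general harm. It makes the expected ratio of windows about 1 and gives a start date to women who never receive a cerclage. If women allocated to laparoscopy conceive later because they wait for surgery, some difference in length would remain, but it would then be a consequence of the allocated strategy and not of the counting rule.

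A pregnancy landmark such as 14+0 weeks, the entry point of the analysis set, is an alternative. Used alone it would create the reverse bias: vaginal procedures near 14 to 16 weeks would put their postoperative events inside the window, while those of a pre-pregnancy laparoscopy would all lie outside it. If it is chosen, events within 30 days of the procedure should be assigned to the surgery-related outcomes only.

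The cost is three changed time-frame lines and a matching date rule in the eCRF. With a randomisation start, some pre-conception events are counted in both arms, and sites must look back to randomisation for bleeding and infection, as they already do for general harm. With the landmark, events between conception and 14+0 drop out of these three outcomes unless they are counted elsewhere. The change should be made before outcomes are compared by arm, so that the window is not chosen with the data in view.

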 - $\circ \quad \text{Time frame: At birth} \\$
- Onset of labour
 - Definition: Spontaneous labor contractions, PROM, induction of labor or c-section.
 - Time frame: At birth
- Mode of birth
 - Definition:
 - Unassisted vaginal

- Assisted vaginal: Ventouse or forceps
- C-section: Planned or non-planned
- o Time frame: At birth

Neonatal outcomes

- Modified Neonatal mortality
 - \circ Definition: Death of a liveborn child \geq 22+0 weeks of gestation
 - \circ ~ Time frame: From birth to four weeks after expected due date
- Neonatal mortality
 - Definition: Death in the 1st 28 days of life > 22+0 weeks of gestation
 - Time frame: 28 days post delivery
- Fetal loss
 - Definition: Composite of late miscarriage (14+0 22+0 weeks of gestation) and stillbirth ($\geq 22+0$ weeks where baby dies before or during delivery)
 - Timeframe: At expected due date
- Late miscarriage
 - Definition: Delivery between 14+0 21+6 weeks of gestation
 - Time frame: At expected due date
- Gestational age at birth[9]
 - Definition: Weeks and days
 - \circ ~ Time frame: At birth
- Preterm birth < 28 weeks
 - Definition: Delivery before < 28 weeks + 0 days
 - Time frame: At birth
- Preterm birth < 34 weeks
 - Definition: Delivery before 34 weeks + 0 days
 - Time frame: At birth
- Preterm birth < 37 weeks
 - Definition: Delivery before_37 weeks + 0 days
 - Time frame: At birth
- Birthweight [9]
 - o Definition: Grams
 - Time frame: At birth
- Neonatal admission
 - Definition: Number of consecutive days in hospital within 28 days from delivery. Any admission counts (SCBU, maternity ward, NICU)
 - Time frame: Post delivery
- CNS morbidity[9]
 - Definition:
 - Intraventricular Hemorrhage Grade III and IV (yes/no)
 - Periventricular leukomalacia (yes/no)
 - Time frame: At four weeks after expected due date

- Ocular morbidity
 - Definition: Retinopathy requiring treatment
 - Time frame: At four weeks after expected due date
- Gastrointestinal morbidity[9]
 - Definition: Necrotizing enterocolitits (NEC) requiring surgery (Bells stage 3) and/or spontaneous intestinal perforation (SIP) requiring surgery
 - Time frame: At four weeks after expected due date
- Respiratory support
 - o Definition: Mechanical ventilation or non-invasive ventilation (NIV)
 - Time frame: At four weeks after expected due date
- Respiratory Distress Syndrome (RDS)
 - Definition: Surfactant treatment
 - Time frame: 2 days of life
- Early onset infection

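### Neonatal morbidity outcomes leave out death, but the stated analysis set holds every pregnancy beyond 14+0, so read literally losses count as non-events

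*Protocol*

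**What the plan says.** Section 12 (Neonatal outcomes) defines each morbidity only by the condition or treatment occurring. CNS morbidity has two items, "Intraventricular Hemorrhage Grade III and IV (yes/no") and "Periventricular leukomalacia (yes/no"). Respiratory support is "Mechanical ventilation or non-invasive ventilation (NIV"). Ocular and gastrointestinal morbidity, respiratory distress syndrome and early infection are defined in the same manner. Most carry the line "Time frame: At four weeks after expected due date"; respiratory distress syndrome is timed at two days of life. None includes death, and none is limited to live births, although modified neonatal mortality in the same list is limited to live-born children.

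Section 21 sets the population: "All primary analyses (primary and secondary outcomes) will be conducted on a modified intention-totreat basis". That set consists of women pregnant at randomisation, or who become pregnant "after randomisation and carry a pregnancy beyond 14+0 weeks". Of this set it adds that "all participants shall be included whether or not they received the allocated intervention". Other secondary outcomes are exploratory, without adjustment for multiplicity.

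Death is counted elsewhere in Section 12: as baby death (the second prioritised primary outcome), fetal loss, late miscarriage and two neonatal mortality outcomes.

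**The concern.** A pregnancy lost at 18 weeks cannot lead to treated retinopathy or surgical enterocolitis, yet Section 21 keeps it in the denominator. Taken together, the definitions and the population count such a loss as free of morbidity. Death is a competing event here, and the trial is planned on the arms differing in it: Section 15 plans for a 15-point difference in baby death.

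The obvious alternative, live births only, departs from the population in Section 21. It also conditions on something that the treatment is expected to change, so it no longer compares the randomised groups.

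Section 7 makes adverse neonatal outcomes part of the full-trial objective. At stake is a morbidity table in which the arm with more losses looks healthier than it is.

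**Working it through.** **The plan's own figure.** Inputs from Sections 15 and 21: 20% vs 5% delivering before 32+0, two-sided alpha 0.05, power 80%, 1:1 allocation.

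- n per arm = [1.96 × √(2 × 0.125 × 0.875) + 0.842 × √(0.20 × 0.80 + 0.05 × 0.95)]² / 0.15² = 75.1, so 76.
- After two 10% inflations: 76 / (0.9 × 0.9) = 93.8, so 94 per arm and 188 in total. This matches the protocol. The point does not touch the sample size; 76 evaluable women per arm is used below for counts.

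**Distortion if losses and deaths count as non-events.** Let d be the baby-death rate in an arm and m the morbidity rate among survivors. The protocol gives no m, so m is assumed equal in both arms. For simplicity, no infant who dies is counted with morbidity.

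- Morbidity alone, whole set: (1 − d) × m.
- Laparoscopic/vaginal risk ratio: (1 − d_lap) / (1 − d_vag), which does not depend on m.
- Death or morbidity: d + (1 − d) × m.

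| Baby death, vaginal vs laparoscopic | Source | Risk ratio, morbidity alone | Risk ratio, death or morbidity (m = 2% to 10%) |
|---|---|---|---|
| 21% vs 3% | cited trial, Section 15 | 0.97/0.79 = 1.23 | 0.22 to 0.44 |
| 18% vs 3% | assumed | 0.97/0.82 = 1.18 | 0.25 to 0.49 |
| 10% vs 3% | assumed | 0.97/0.90 = 1.08 | 0.42 to 0.67 |

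Example with m = 5% and deaths 18% vs 3%:

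- Morbidity alone: 0.82 × 5% = 4.1% vaginal vs 0.97 × 5% = 4.85% laparoscopic.
- Death or morbidity: 18% + 4.1% = 22.1% vs 3% + 4.85% = 7.85%, a ratio of 0.36.

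**Would a real benefit be hidden?** Survivor morbidity need not be equal, because the arms are expected to differ in very preterm delivery. Suppose that all deaths follow delivery before 32+0, and that morbidity arises only in survivors born before 32+0, at the same rate in both arms. Per 76 women, deliveries before 32+0 number 76 × 0.20 = 15.2 and 76 × 0.05 = 3.8, a ratio of 0.25.

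- *Pairing these with assumed deaths of 18% vs 3%.* Deaths are 13.7 vs 2.3. Survivors are 15.2 − 13.7 = 1.5 and 3.8 − 2.3 = 1.5, so the morbidity ratio is near 1 and the benefit is hidden.
- *Using the cited trial's death fractions.* These are 21/33 = 64% and 3/8 = 37.5% of deliveries before 32 weeks. Survivors are 15.2 × 0.364 = 5.5 and 3.8 × 0.625 = 2.4, a ratio of about 0.43. The benefit is visible but weaker than the 0.25 for delivery itself. At an assumed 20% to 40% morbidity, this is 1.1 to 2.2 vs 0.5 to 1.0 cases.

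The two pairings give quite different pictures, and the protocol's figures do not settle which applies.

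**The case against.** The protocol nowhere says that a loss is recorded as no morbidity. A reader might infer that from the definitions and the population, but it is a consequence of reading them together, not a stated rule. Section 21 defines a population of women rather than infants, and items timed in days of life or in the first week after delivery presuppose a live birth. Section 21 refers to a fuller analysis plan and Section 18 to a data dictionary, neither of which is shown. Losses could be coded there as missing or not applicable.

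A reader might also infer that every early death counts as free of morbidity. That goes too far: an infant who received surfactant or ventilation, or was found to have a haemorrhage, before dying meets the definition. The problem is certain for late miscarriages and stillbirths and only partial for neonatal deaths. Further, the outcomes are exploratory, case numbers will be very small, and deaths are reported in their own right. A composite would largely repeat baby death.

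Most of this stands and limits the point. It does not remove it. Coding losses as not applicable amounts to a live-birth comparison, which departs from the population fixed in Section 21 and is selected after randomisation. Separate mortality rows do not correct a misleading morbidity ratio. The overlap with baby death is a reason for one composite rather than one for each organ system.

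**Conclusion.** The point holds as an inconsistency between the morbidity definitions in Section 12 and the population in Section 21. Neither the literal reading nor a live-birth restriction gives a sound between-arm comparison of neonatal morbidity.

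Under equal morbidity among survivors, the literal reading moves the laparoscopic/vaginal risk ratio from 1 to 1.23 at the cited death rates, and to 1.18 or 1.08 at the lower assumed rates. A reader might go on to infer that the morbidity results will show no benefit, or harm, from laparoscopic cerclage. The documents do not support that. It depends on pairing 20% vs 5% preterm delivery with 18% vs 3% death, and Section 15 states no arm-specific death rates for this trial. With the cited trial's death fractions a benefit would still show, though attenuated.

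The two prioritised outcomes and the sample size are unaffected. This is a worthwhile, inexpensive improvement to exploratory outcomes and no threat to the main conclusion.

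**What to change.** In Sections 12 and 21, base the between-arm comparison of neonatal morbidity on a single composite: baby death or any listed severe neonatal morbidity. Analyse it in the modified intention-to-treat set, name the qualifying items and show the components. Report each individual morbidity descriptively among live-born infants, beside the number of losses and deaths in each arm. Settle this before outcome data are seen, so that the denominator is not chosen after the fact.

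The cost is a few lines of definition, carried through to the statistical analysis plan; the components are already collected. The drawback is that death will dominate the composite, which overlaps with the second prioritised outcome. It should therefore stay exploratory and outside the hierarchical testing.
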